6.12.2 Clinical Laboratory Tests

Local laboratories were used for this study. Shift tables from baseline to the worst post-baseline values during the randomized treatment period according to the NCI-CTCAE v4.0 toxicity grade will be provided for selected chemistry parameters and hematology parameters. The following categories will be used: \leq Grade II and \geq Grade III. Both scheduled and unscheduled post-baseline values during the randomized treatment period will be considered. Additionally, the number and percentage of subjects with Grade \geq III will be presented for the following hematology tests: White Blood Cell Count (WBC), Hemoglobin, Platelet Count and Absolute Neutrophil Count (ANC).

Laboratory data during the crossover portion will be summarized separately in the same manner.

All clinical laboratory data will be listed by subject. Values outside the normal ranges from local laboratories will be flagged and grades will be displayed for selected parameters. Additionally, the laboratory values will display clinical significance based on investigator judgement.

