9.1 Definitions

9.1.1 Adverse Events

An AE is any untoward medical occurrence in a clinical investigation subject administered an investigational product and which does not necessarily have to have a causal relationship with this treatment. An AE can therefore be any unfavorable and unintended sign (including an abnormal laboratory finding, for example), symptom or disease temporally associated with the use of an investigational product, whether or not considered related to the investigational product.

The description of each AE will identify the subject, date of onset, the date of resolution, the severity of the event, the action taken regarding study drug, the outcome of the event, and the relationship of the event to study drug. A medical condition present at screening that has increased in frequency or severity must be recorded on the AE page of the eCRF.

Standard medical terminology should be used to document AEs on the eCRF. The subject's exact description of the event will be recorded in the source documentation. In the case of signs and symptoms, the underlying illness or diagnosis will be recorded as the event when known.

For this study, disease progression will not be considered as an AE. Lymphopenia is the pharmacologic effect of the drug and will also not be considered an AE for this study. Lymphocytes will be monitored and evaluated with the laboratory data.

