10.2 Analyses of Safety Data

The safety and tolerability of KW-0761 and vorinostat is determined by reported AEs, physical examinations, ECGs, vital signs, and laboratory tests. All summaries for the Safety Analysis Set will be prepared for each treatment arm. For those subjects in the vorinostat arm who cross over to KW-0761 treatment arm, AEs with an onset date/time after the first dose of KW-0761 will be summarized separately within that KW-0761 crossover group.

The World Health Organization (WHO) Drug Dictionary will be used to classify prior and concomitant medications by therapeutic class and Preferred Term. Prior medications include medications that were taken within 30 days prior to the Pre-treatment Visit. Concomitant medications include medications that started at any time and were taken at any time after the start of treatment until the end of the entire treatment period.

Adverse events are collected from the time the subject signs the ICF until 90 days after the last dose or initiation of alternative therapy, whichever comes first. In all subjects who cross over from vorinostat to KW-0761, the causality should be assessed for both drugs for 30 days after vorinostat was stopped (or later if the event is considered to be related to vorinostat). The NCI-CTCAE v4.0 system will be used to grade AEs. Treatment-emergent AEs will be grouped and tabulated by MedDRA preferred terms and system organ class. AEs will be

classified by body system, incidence, severity, and causality. All treatment-emergent AEs will be summarized showing the number and percent of subjects for each outcome.

The results from physical examination will be presented in the subject data listings. Vital sign measurements will be summarized at each time point. The incidence of clinically significant laboratory abnormalities will be presented, and laboratory data will be summarized at each time point by the NCI-CTCAE v4.0 toxicity grade. Laboratory data will be presented for subjects having Grade 3 or 4 changes from baseline by treatment arm.

Pre- and post-treatment serum samples will be assayed for development of human antibodies to KW-0761 (anti-KW-0761).

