Vorinostat (N=xx)	xx	<=Grade II	xx (xx.x)	xx (xx.x)	xx (xx.x)
		>=Grade III	xx (xx.x)	xx (xx.x)	xx (xx.x)
		Total	xx (xx.x)	xx (xx.x)	xx (xx.x)
KW-0761 (N=xx)	xx	<=Grade II	xx (xx.x)	xx (xx.x)	xx (xx.x)
		>=Grade III	xx (xx.x)	xx (xx.x)	xx (xx.x)
		Total	xx (xx.x)	xx (xx.x)	xx (xx.x)
Etc.					

Note: Percentage is calculated using N' as the denominator where N' is the number of subjects with both baseline and post baseline measurements for the specified parameter.

<<Programming Note: parameters in this table include: AST, ALT, Alkaline Phosphatase, Albumin, Creatinine, Glucose, Total Bilirubin, Phosphorus, and Magnesium. High shifts and low shifts will be summarized for parameters with separate CTC grade criteria for low values and high values (i.e., Glucose and Magnesium).>>

Table 14.3.4.2
 Shift Table for Selected Laboratory Parameters During Randomized Treatment Period - Hematology
 Safety Analysis Set

Parameter (Unit) Treatment Arm	N'	Baseline	---- Highest CTCAE Grade During Randomized Treatment Period ----		
			<=Grade II	>=Grade III	Total
XXX (Unit)					
Vorinostat (N=xx)	xx	<=Grade II	xx (xx.x)	xx (xx.x)	xx (xx.x)
		>=Grade III	xx (xx.x)	xx (xx.x)	xx (xx.x)
		Total	xx (xx.x)	xx (xx.x)	xx (xx.x)
KW-0761 (N=xx)	xx	<=Grade II	xx (xx.x)	xx (xx.x)	xx (xx.x)
		>=Grade III	xx (xx.x)	xx (xx.x)	xx (xx.x)
		Total	xx (xx.x)	xx (xx.x)	xx (xx.x)
Etc.					

Note: Percentage is calculated using N' as the denominator where N' is the number of subjects with both baseline and post baseline measurements for the specified parameter.

<<Programming Note: parameters in this table include: Hemoglobin, WBC, Platelet Count, Lymphocytes, ANC, and CD4. >>

The following tables will have similar layout as Tables 14.3.4.1 and 14.3.4.2:

Table 14.3.4.3
Shift Table for Selected Laboratory Parameters During Crossover Portion - Serum Chemistry
Safety Analysis Set
Subjects Who Are Randomized to Vorinostat and Crossed Over to KW-0761

Table 14.3.4.4
Shift Table for Selected Laboratory Parameters During Crossover Portion - Hematology
Safety Analysis Set
Subjects Who Are Randomized to Vorinostat and Crossed Over to KW-0761

<<Programming Note: For tables 14.3.4.3 and 14.3.4.4, the highest CTC/AE Grade during Crossover Period will be presented.>>

Table 14.3.4.5
 Number (%) of Subjects with Grade \geq III Laboratory Values for Selected Hematology Parameters
 Safety Analysis Set

Period Parameter	Vorinostat	KW-0761
	N=xx n/N' (%)	N=xx n/N' (%)
During Randomized Treatment Period		

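### Laboratory grades are summarized only as Grade II or lower versus Grade III or higher, an unflagged departure from Protocol 10.2 that matters mainly for lymphocytes and CD4

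*SAP*

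**What the plan says.** **Protocol.** Section 10.2 states that "laboratory data will be summarized at each time point by the NCI-CTCAE v4.0 toxicity grade". Later in the same paragraph it adds a second display: "Laboratory data will be presented for subjects having Grade 3 or 4 changes from baseline by treatment arm". Section 9.1.1 says "Lymphopenia is the pharmacologic effect of the drug and will also not be considered an AE for this study", and then "Lymphocytes will be monitored and evaluated with the laboratory data".

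**SAP.** Section 6.12.2 plans shift tables from baseline to the worst post-baseline value, graded by CTCAE v4.0, and fixes the classes: "The following categories will be used: \leq Grade II and \geq Grade III". The shells for Tables 14.3.4.1 (chemistry) and 14.3.4.2 (hematology) print this layout. Tables 14.3.4.3 and 14.3.4.4 repeat it for the crossover portion. The programming note to Table 14.3.4.2 says "parameters in this table include: Hemoglobin, WBC, Platelet Count, Lymphocytes, ANC, and CD4". Table 14.3.4.5 counts subjects at Grade III or higher, for WBC, hemoglobin, platelets and ANC only.

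The list of tables in SAP Section 9 has no other laboratory summary. Individual values are listed by subject, with grades for selected parameters. SAP Section 1 lets the SAP supersede the protocol's statistical text but says substantially different considerations will be identified. Section 6.12.2 identifies none.

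**The concern.** Further assessment of KW-0761 safety is a stated secondary objective. For most laboratory parameters a coarse shift table is backed up by the adverse event tables by highest grade. For lymphocytes the protocol removes that backup and relies on the laboratory data. The table that then has to show them cannot separate Grade 3 from Grade 4, or show movement below Grade 3.

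The protocol itself treats the depth of T-cell depletion as worth tracking: Section 7.5 continues follow-up when CD4 and CD8 counts are below 200/mm³ at the End-of-treatment visit. The SAP gives infections exposure-adjusted rates in Section 6.12.1, but provides no graded lymphocyte or CD4 summary to read beside them. Nor is a two-class shift the SAP's general style: the QTc shift table in Section 6.12.4 uses four ordered categories.

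**Working it through.** The plan states no figure to reproduce. The check has two parts.

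**1. Where each parameter can appear in a summary table**

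| Parameter | Two-class shift (14.3.4.2, 14.3.4.4) | Grade III or higher count (14.3.4.5) | TEAE table by highest grade (14.3.1.4) |
|---|---|---|---|
| Platelets, ANC, WBC, hemoglobin | yes | yes | yes, if reported as an AE |
| Lymphocytes | yes | no | no: lymphopenia is not an AE (Protocol 9.1.1) |
| CD4 | yes | no | not settled: the exclusion names lymphopenia, not CD4 counts |

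For lymphocytes, the two-class shift tables are the only graded summary. For CD4, they are the only laboratory summary.

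**2. What two classes can and cannot show**

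Input: grades 0 to 4, five levels. This is an assumption. The documents do not spell out a laboratory scale, but Protocol 10.2 speaks of Grade 3 or 4 laboratory changes, and Protocol 9.1.2 defines Grade 5 as death related to an AE. Grade 0 (no graded abnormality) has to sit in the lower class, because the shell's percentages use every subject with a baseline and a post-baseline value.

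- Possible worsenings (baseline grade below worst grade): 5 × 4 / 2 = 10.
- Within {0, 1, 2}: 3 × 2 / 2 = 3 (0→1, 0→2, 1→2).
- Within {3, 4}: 1 (3→4).
- Printed as no shift: 3 + 1 = 4 of 10.
- Printed as a shift: 3 × 2 = 6 of 10. All six fall in the same cell, so 0→3 and 0→4 look alike.

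Sensitivity to the scale:

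| Top grade | Possible worsenings | Within one class | Share |
|---|---|---|---|
| 3 | 6 | 3 | 50% |
| 4 | 10 | 4 | 40% |
| 5 | 15 | 6 | 40% |

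With each grade as its own row and column, 0 of 10 are hidden.

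A 3→4 shift is not excluded by design. The general hematology eligibility criterion sets floors for ANC and platelets but not for lymphocytes. A CD4 floor applies only after earlier anti-CD4 antibody or alemtuzumab.

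**The case against.** The strongest reply is that the SAP keeps a good part of the protocol's plan. A baseline-to-worst shift split at Grade III is close to the second display in Protocol 10.2, subjects with Grade 3 or 4 changes by arm. All values remain in the listings, and T-cell counts have their own. Since the protocol calls lymphopenia the drug's pharmacologic effect, a display centered on severe falls is defensible. SAP Section 1 also permits supplementary analyses.

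Most of this stands, and it rules out some stronger readings:

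- A reader might infer that the SAP discarded the protocol's laboratory plan. It did not. It kept a display near the Grade 3 or 4 one and left out the by-grade, by-visit one. Superseding the protocol is allowed; what is missing is the statement that it was done.
- A reader might infer that mild platelet falls on vorinostat vanish from the summaries. They need not. Laboratory AEs are graded, and Table 14.3.1.4 shows Grades I to V separately. The falls lost are those never reported as AEs. The minimum capture rule in Protocol 7.1.1 (events that are serious, stop or interrupt drug, or need corrective therapy) does not require every mild fall to be reported.
- A reader might infer that lymphocyte toxicity goes unreported. Grade III or higher counts appear by arm in Table 14.3.4.2, and the values are in the listings.

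What the reply does not answer is that, for lymphocytes and CD4, no laboratory summary table separates Grade 3 from Grade 4 or shows worsening within Grades 0 to 2.

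**Conclusion.** The point holds, as a minor one about safety reporting. SAP 6.12.2 omits the by-grade, by-visit laboratory summary in Protocol 10.2 without identifying the difference. For lymphocytes and CD4, no other laboratory summary table fills the gap.

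Four of ten counts types of transition, each weighted equally, on an assumed 0 to 4 scale (40% to 50% under the alternatives). A reader might take it to mean that 40% of worsening patients are hidden. The documents give no frequencies, so nothing supports that reading.

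The conclusion rests on three assumptions:

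- Protocol 9.1.1 keeps lymphopenia out of the AE tables in practice.
- The SAP's list of tables is complete.
- The sentence in Protocol 10.2 was already present when the SAP was written. The SAP cites amendments up to No. 7, while the protocol in hand refers to Amendment 10.

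The primary PFS analysis and the key secondary efficacy analyses are unaffected.

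**What to change.** 1. In Tables 14.3.4.2 and 14.3.4.4, use Grades 0, 1, 2, 3 and 4 as rows and columns, at least for lymphocytes and CD4 and preferably for all parameters in Tables 14.3.4.1 to 14.3.4.4. Keep the Grade III or higher count as a summary line.
2. Finer shift tables do not restore the time-point element. Either add the by-visit, by-grade summary, or state in SAP 6.12.2 that it is omitted and that this departs from Protocol 10.2.

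Cost: no new data are needed, and the shell column is already headed by highest CTCAE grade. The body of each shift grows from 4 cells to 25 per parameter and arm, before totals. Limited to lymphocytes and CD4, that is a small change. Extended to all nine chemistry and six hematology parameters, with separate high and low shifts for glucose and magnesium and again for crossover, the tables become noticeably longer. Stating the omission takes one sentence; the by-visit summary would be an added table.

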6.12.3 Vital Signs

Vital signs measurements including pulse rate, respiratory rate, temperature, systolic blood pressure, diastolic blood pressure, and body weight will be summarized descriptively (n, mean, standard deviation, median, minimum, and maximum). Baseline and changes from baseline to end of treatment will be presented during the randomized treatment period by treatment arm. Additionally the maximum and minimum post-treatment values during the randomized treatment period will be summarized by treatment arm. Vital signs during the crossover portion will be summarized separately in the same manner.

All vital signs measurements will be listed by subject.

6.12.4 12-Lead Electrocardiogram (ECG)

The QTc intervals are to be determined using the Fridericia correction (QTcF) and the Bazett correction (QTcB). The QTcF and QTcB intervals of the ECG measurements and changes from baseline to end of treatment during the randomized treatment period will be summarized by treatment arm. The number and percentage of subjects with elevated QTcF or QTcB values (> 450 msec, > 480 msec, and > 500 msec) at baseline and end of treatment during the randomized treatment period will be presented by treatment arm. In addition, the number and percentage of subjects with QTcF or QTcB values that increase by > 30 msec and > 60 msec from baseline to end of treatment will also be presented by treatment arm.

A shift table from baseline to the worst post-baseline values during the randomized treatment period will be provided for QTcF and QTcB intervals. The following categories will be used: ≤ 450 msec, > 450 and ≤ 480 msec, > 480 and ≤ 500 msec, and > 500 msec.

All ECG measurements and the overall interpretation will be listed by subject. Abnormal QTcF or QTcB values will be flagged in the listing.

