- a: If progression is noted at Day 26-28, visit should take place before initiation of new therapy. In cases where the definition of PD or relapse is met but the clinical impression is questionable, subjects may remain on study until the next evaluation (4 weeks later if questionable finding in skin or blood; 8 weeks later in first year and 16 weeks later after Year 1 if questionable finding in lymph nodes or viscera, with at least stable disease in other compartments) to avoid a subject being removed prematurely from the study. For subjects receiving a subsequent treatment course, procedures performed at this time can also be used to satisfy the Day 1 requirements for the subsequent course, provided they are performed within ± 2 days of next KW-0761 administration. For subjects who will not receive subsequent treatment, this visit will be considered the final treatment visit and subjects should undergo testing/procedures specified for End-of-treatment visit (See Table 3).
- b: Complete physical examination including height at Pre-treatment Visit; brief physical examination of pertinent systems at other times. Responses to questions for surveillance of autoimmune type symptoms (See Appendix 4) should be documented at time of physical exam.
- c: For subjects receiving KW-0761, vital signs will be checked and recorded prior to the start of each infusion, at the end of each infusion and 1 hour after the completion of the infusion. For subjects taking vorinostat, vital signs can be taken irrespective of dosing. Weight will be checked with vitals.
- d: Blood can be drawn 1 day prior to visit, if needed, to ensure results are available. In subjects receiving KW-0761, results must be reviewed prior to infusion. The platelet count must be $\geq 100,000 / \text{mm}^3$ and the ANC must be $\geq 1,500/\text{mm}^3$ before a subject can receive study drug.
- e: Serum samples will be collected for subjects treated with KW-0761 pre-dose on days indicated (sample collection will still be needed even if dosing is not performed at a visit), as applicable. On Day 1, an additional sample should be obtained from the arm contralateral to that of study drug administration at the end of infusion (10-15 minutes after completion of the infusion) as well. At selected sites, 4 additional samples will be drawn between 6 and 8 hours, and at 24, 48, and 72 - 96 hours after the first infusion on Day 1.

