Footnotes to Table 2 (continued).

- b: For subjects receiving a subsequent treatment course, procedures performed at this time can also be used to satisfy the Day 1 requirements for the subsequent course, provided they are performed within ± 2 days of next KW-0761 administration. For subjects who will not receive subsequent treatment, this visit will be considered the final treatment visit and subjects should undergo testing/procedures specified for End-of-treatment visit (See Table 3). If progression is noted at Day 26-28, visit should take place before initiation of new therapy. In cases where the definition of PD or relapse is met but the clinical impression is questionable, subjects may remain on study until the next evaluation (4 weeks later if questionable finding in skin or blood; 8 weeks later in first year and 16 weeks later after Year 1 if questionable finding in lymph nodes or viscera, with at least stable disease in other compartments) to avoid a subject being removed prematurely from the study.
- c: Brief physical examination of pertinent systems to be performed during subsequent treatment cycles. Complete physical exam to be performed at End of Treatment visit. Responses to questions for surveillance of autoimmune type symptoms (See Appendix 4) should be documented at time of physical exam.
- d: For subjects receiving KW-0761, vital signs will be checked and recorded prior to the start of each infusion, at the end of each infusion and 1 hour after the completion of the infusion. For subjects taking vorinostat, vital signs can be taken irrespective of dosing. Weight will be checked with vitals.
- e: Blood can be drawn 1 day prior to visit, if needed, to ensure results are available. In subjects receiving KW-0761, results must be reviewed prior to infusion. The platelet count must be $\geq 100,000 / \text{mm}^3$ and the ANC must be $\geq 1,500/\text{mm}^3$ before a subject can receive study drug.
- f: If clinical progression is noted at any time prior to the scheduled assessments for efficacy, CT, mSWAT, skin photographs and flow cytometry assessments should be done at that time to fully document disease progression, i.e., Global Composite Response Score. CT must be performed even if previously negative at baseline.
- g: Serum samples for PK assessment should be collected for subjects treated with KW-0761 prior to infusion of KW-0761 in Cycles 2 and 3 (sample collection will still be needed even if dosing is not performed at a visit).

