- h: KW-0761 is to be administered over at least one hour.
- i: Vorinostat is administered orally daily beginning on Day 1 with food.
- j: If a subject who is receiving KW-0761 develops a skin rash, notify KKD and refer to Section 5.2.1.8 to treat and document the rash.
- k: Medication taken at any time after the start of treatment until 30 days after the final study drug administration will be recorded.
- l: To be performed in subjects with cytopenia or other clinical suspicions of bone marrow involvement, at the discretion of the investigator. If a bone marrow biopsy was performed at baseline and determined to unequivocally be indicative of lymphomatous involvement, then to confirm a global CR where blood assessment now meets criteria for B0, a repeat bone marrow biopsy must show no residual disease or the response should be considered a PR only (See Table 7.2.2-1).
- m: Biopsies at the end of the cycle and to confirm a CR (See Table 7.2.1-3) are optional and can be performed at the discretion of the investigator. Analysis of these biopsies will be done by a pathologist at the study site.
- n: KW-0761 subjects only for determination of anti-KW-0761 antibodies and concentration of KW-0761.
- o: Subjects who terminate for reasons other than disease progression or their referring physicians will be contacted every 3 months (± 14 days) until documented disease progression or death or initiation of alternative therapy.
- p: All subjects or their referring physician will be contacted every 3 months (± 14 days) to ascertain survival status following discontinuation of treatment.

Table 3 Study Procedures: Subsequent Cycles in Year 2 and Beyond^a

Procedures	D 1	D 15	D 26-28 (Cycles 14, 16, 18, 20, etc) ^b	D 26-28 (Cycles 15, 17, 19, 21, etc) ^b	D 26-28 Q 16 wks (Cycles 17, 21, etc)	End-of- treatment visit	Follow- up ^c
Visit Window		± 2 days	+ 2 days	+ 2 days	+ 5 days	Within 30 days of last dose	
Physical examination ^d	X	X	X	X		X	
ECOG PS	X	X	X	X		X	
Vital signs, Weight	X ^e	X ^e	X	X		X	
ECG						X	
Urinalysis	X					X	
Hematology profile	X ^f	X ^f	X	X		X	
Chemistry profile	X ^f	X ^f	X	X		X	
Coagulation profile	X ^f						
Thyroid function tests (Free T4, TSH)				X		X	
Flow Cytometric Analysis ^g			X	X			
Blood sample for determination of natural ligands				X			
Serum sample for KW-0761 concentration assessment						X	
KW-0761 Administration	X ^h	X ^h					
Vorinostat Administration	X ⁱ						
Adverse event assessment ^j	X	X	X	X		X	X ^k

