5.2.1 Study Drug: KW-0761 (mogamulizumab)

Treatment can be administered on an outpatient basis. Subjects will receive 1.0 mg/kg of KW-0761 as an iv infusion over at least 1 hour on Days 1, 8, 15, and 22 of the first cycle and on Days 1 and 15 of subsequent cycles. No other investigational or commercial agents or therapies other than the study treatment and those described in Section 5.4.1 may be administered with the intent to treat the subject's malignancy.

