8.1.3 Study Drug Administration

Subjects will receive KW-0761 as an iv infusion over at least 1 hour for all infusions. Subjects will be observed closely for 1 hour following each administration of KW-0761 for

any potential AEs in an area with resuscitation equipment. Vital signs will be checked and recorded prior to start of infusion, at the end of the infusion and at 1 hour after completion of infusion.

Hematology results should be reviewed before each subsequent dose. Laboratory assessments may be performed the day prior to dosing to ensure results are available prior to dosing. The platelet count must be $\geq 100,000 / \text{mm}^3$ and the ANC must be $\geq 1,500/\text{mm}^3$ before a subject can receive study drug. If a scheduled dose cannot be given within the allowed window, the dose should be skipped and the subject should resume dosing with the next scheduled dose assuming the platelet count and ANC are within the parameters described above. If a subject misses 2 consecutive doses, contact the Medical Monitor or designee to determine if the subject should be withdrawn from the trial.

Should a hypersensitivity reaction to KW-0761 occur, the subject must be treated according to the best available medical practices. Subjects should be instructed to report any delayed reactions to the investigator immediately. See Section 5.2.1.7 for additional information regarding the treatment of infusion reactions.

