9.3 Other Safety Considerations

Any clinically important changes noted during interim or final physical examinations, ECGs, x-rays, or any other potential safety assessments, whether or not these procedures are required by the protocol, must also be recorded on the appropriate eCRF page and SAE form, as appropriate, in order for the Sponsor to collect additional information about that abnormality, including information regarding relationship to study drug, any action taken, and resolution.

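### The by-arm maximum and minimum vital-sign rows are not like for like: KW-0761 has three readings per infusion, vorinostat has no repeats specified

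*SAP*

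**What the plan says.** SAP 6.12.3, on the vital-sign tables: "Additionally the maximum and minimum post-treatment values during the randomized treatment period will be summarized by treatment arm". The shell of Table 14.3.5.1 has four blocks per parameter: baseline, maximum post-baseline, minimum post-baseline and end of treatment. The parameters are pulse rate, systolic and diastolic pressure, temperature, respiratory rate and weight. Neither the text nor the shell restricts the extremes to a time point or reduces repeats within a visit to one value.

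For KW-0761, protocol 8.1.3 has vital signs "recorded prior to start of infusion, at the end of the infusion and at 1 hour after completion of infusion". Footnote c to Table 1 and footnote d to Table 2 say the same. Infusions are given "on Days 1, 8, 15, and 22 of the first cycle and on Days 1 and 15 of subsequent cycles" (protocol 5.2.1). For the comparator, the same footnotes say only: "For subjects taking vorinostat, vital signs can be taken irrespective of dosing".

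Mock Listing 16.2.8.16 matches this. A KW-0761 infusion visit has three rows with time-point codes 1, 2 and 3. A vorinostat visit has one row and no code. Weight appears only on the pre-infusion row of the infusion visit.

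**The concern.** The expected maximum of a set of readings rises with the number of readings, and the expected minimum falls, with no treatment effect at all. Here the number of readings differs between arms by design. The two rows move in opposite directions at once, which a reader could take for unstable pulse or blood pressure after an antibody infusion.

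Apart from baseline and end of treatment, these rows are the only between-arm vital-sign summary. A reader could mistake a reading-count difference for a drug effect. Equally, a reader who knows of the imbalance could discount a real effect, because the table gives no way to separate the two.

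**Working it through.** The plan states no figure for this point, so there is none to reproduce.

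**Extra readings.** Each infusion adds 2 readings beyond a single visit reading. Six cycles have 4 + 5 × 2 = 14 infusions, so KW-0761 has 2 × 14 = 28 extra. This needs no visit grid, only that both arms attend the same visits and that vorinostat has one reading per visit.

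**Total readings.** The grids of Tables 1 and 2 are not in the available text. The Table 3 pattern ("Subsequent Cycles in Year 2 and Beyond") is assumed to hold in Year 1. Post-baseline readings over six cycles:
- KW-0761: Cycle 1 is 2 + 3 + 3 + 3 + 1 = 12 (the Day 1 pre-infusion reading is baseline). Five later cycles of 3 + 3 + 1 = 7 give 35. End of treatment adds 1. Total 48.
- Vorinostat: 4 in Cycle 1, 5 × 3 = 15 later, 1 at end of treatment. Total 20.

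**Size with no drug effect.** Take reading j at visit v as Y = d + e, with d normal with variance ρ (shared within the visit) and e normal with variance 1 − ρ. The unit is the within-subject SD. The quantity is E[max of 48] − E[max of 20], simulated with 120,000 draws:

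| Within-visit correlation ρ | 0 | 0.7 | 0.8 | 0.9 | 0.95 |
|---|---|---|---|---|---|
| Difference in mean maximum (SD) | 0.366 | 0.275 | 0.236 | 0.182 | 0.136 |

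A separate run of 20,000 subjects gave mean maxima of 2.14 v 1.87 at ρ = 0.7 and 2.05 v 1.87 at ρ = 0.9, that is, differences of 0.27 and 0.18. By symmetry the minimum shifts by the same amount downwards.

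**Sensitivity to the reading counts** (ρ = 0.95 to 0.7):
- Sparsest grid, 42 v 14: 0.19 to 0.36 SD.
- One more visit per cycle, 54 v 26: 0.11 to 0.22 SD.
- Vorinostat read twice per visit, 48 v 40: 0.03 to 0.05 SD.

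**In mmHg.** The documents give no vital-sign SD. If the within-subject systolic SD were 8 to 12 mmHg (assumed), the shift would run from 0.14 × 8 = 1.1 to 0.27 × 12 = 3.2, or about 1 to 3 mmHg.

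**Time on treatment.** Using the planned median PFS (254 v 169 days) as exponential time on treatment, an assumption, the total difference is 0.25 to 0.39 SD. About 0.14 to 0.27 comes from reading frequency and about 0.12 from longer treatment.

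**With one reading per visit.** At six cycles in each arm the counts are 20 v 20 and the difference is 0. Under the planned medians, 0.134 SD remains from longer treatment, or 0.056 SD if both arms are cut at six cycles.

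**The case against.** An all-readings worst value is a conventional safety summary. The SAP uses worst post-baseline values for laboratory grades (6.12.2) and QTc (6.12.4), and every such summary depends on how often and how long subjects are measured. The end-of-infusion and 1-hour readings are the ones most likely to show a real infusion effect. Dropping them from the only between-arm extreme rows could hide the extremes they are there to catch. This stands, and it is why the existing rows should stay. It does not make them like for like: here one arm's repeats are built into the schedule, whereas protocol 7.1.4 sets one ECG schedule for both arms.

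The size is largely assumed. Visit grid, correlation and SD are not in the available text, and a second vorinostat reading per visit would nearly remove the effect. This also stands. Direction and mechanism come from the documents; the magnitude is a range under assumptions.

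Three stronger readings are tempting, and the documents support none of them:
- A reader might infer that any difference in these rows is artefact. Real infusion effects and time on treatment also feed them, so reading frequency is one component.
- A reader might infer that infusion effects could go undetected. Infusion reactions are recorded as adverse events and appear in Tables 14.1.5 and 14.3.8.2 and Listing 16.2.5.1. Protocol 9.3 also requires recording of "Any clinically important changes noted during interim or final physical examinations, ECGs, x-rays, or any other potential safety assessments".
- A reader might infer a breach of protocol 10.2 ("Vital sign measurements will be summarized at each time point"), since SAP 6.12.3 has no by-visit summary. The SAP Introduction says it supersedes the protocol's statistical considerations, so this is at most a documentation point.

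**Conclusion.** The point holds, at low priority. For pulse, respiratory rate, temperature and blood pressure, following the SAP exactly gives a between-arm difference in the extreme rows with no drug effect. Weight is probably unaffected, because the mock listing shows it once per infusion visit. Baseline and end-of-treatment rows use one value per subject and are unaffected. Crossover Table 14.3.5.2 has one group, so no between-arm comparison arises there.

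The likely size is 0.14 to 0.27 within-subject SD in each direction at six cycles per arm. This assumes one vorinostat reading per visit, shared visits on the Table 3 pattern and within-visit correlation of 0.7 to 0.95. The consequence is limited to how one descriptive table is read; no test or decision rule uses these rows.

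**What to change.** In SAP 6.12.3 and Table 14.3.5.1:
- Keep the all-readings maximum and minimum rows in both arms, labelled as the worst-value safety summary.
- Add between-arm maximum and minimum rows based on one reading per scheduled visit, using time point 1 (pre-infusion) for KW-0761.
- Footnote the scheduled readings per visit in each arm.

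A common window such as Cycles 1 to 6, and a KW-0761 table of change from pre-infusion to end of infusion and to 1 hour, are optional.

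The cost is SAP wording and two more rows per parameter. The readings are already scheduled, and the mock listing already carries the time-point codes, so no new data are needed. The new rows remove the reading-frequency component but not differences in time on treatment: about 0.13 SD under the planned medians used as exposure, or about 0.06 SD with a six-cycle window, which would discard later extremes from those rows.
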